## **Collaboration and interaction**

The goals of telehealth monitoring are better patient experience, better (or more stable) physical and mental health, and lower costs for the health care services. One way to achieve these goals is by better collaboration and collaboration between different parts of the health care services.

In this section, we ask how you feel that the collaboration with other health care services related to telehealth monitoring works.

24. How often do you contact the follow-up service in the following situations?

- Recruitment of patient / user for the trial
  - Never
  - Less than once per month
  - 1-2 times per month
  - 3-4 times per month
  - More than 4 times a month
- Design of follow-up plan for patient / user participating in the trial
  - Never
  - Less than once per month
  - 1-2 times per month
  - 3-4 times per month
  - More than 4 times a month
- Follow-up of patient / user participating in the trial
  - Never
  - Less than once per month
  - 1-2 times per month
  - 3-4 times per month
  - More than 4 times a month

25. How does telehealth monitoring affect your interaction with:?

- Home nursing care unit
  - Much worse interaction
  - Somewhat worse interaction
  - No change in interaction
  - Some better interaction
  - Much better interaction
- Specialist health service

- Much worse interaction
- Somewhat worse interaction
- No change in interaction
- Some better interaction
- Much better interaction

26. How do you feel that telehealth monitoring affects the coordination and consistency of the service provision of the individual patient?

- I find that the degree of coordination and coherence is reduced
- I find that there is no change in the degree of coordination and context
- I find that the degree of coordination and coherence is increasing

27. Do you have any other comments related to the interaction with other healthcare providers?

#### **Satisfaction with and benefits of telehealth monitoring for patients/users**

In this section, we ask about how you perceive that telehealth monitoring affects the users.

28. To what extent do you feel that the users are satisfied with telehealth monitoring?

- Not at all
- To a small extent
- To some extent
- To a large extent
- Do not know

29. To what extent do you feel that telehealth monitoring contributes positively to users ...?

- Physical health
  - Not at all
  - To a small extent
  - To some extent
  - To a large extent
  - Do not know
- Mental health
  - Not at all
  - To a small extent
  - To some extent
  - To a large extent
  - Do not know
- Security
  - Not at all
  - To a small extent
  - To some extent
  - To a large extent
  - Do not know
- Coping with own illness
  - Not at all
  - To a small extent
  - To some extent
  - To a large extent
  - Do not know

30. To what extent do you feel that telehealth monitoring helps patients / users become more involved in the follow-up of their own illness?

- Not at all
- To a small extent
- To some extent
- To a large extent
- Do not know

31. Do you experience a change in the proportion of immediate help appointments among patients receiving telehealth monitoring?

- I experience a reduction in the proportion of immediate help appointments
- I do not experience any change
- I experience an increase in the proportion of immediate help appointments

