## 6.5 Cost-benefit analysis

In Norway, cost-benefit analyses are used to inform decision making and prioritization across all sectors of the economy. The purpose of this cost-benefit analysis is to assess the overall benefits and costs of the use of telehealth. This analysis will also elucidate distributional effects and an assess the societal value of telehealth (including an assessment of which factors are essential in ensuring the value of telehealth).

The analysis will use data obtained in the effectiveness study and in the process evaluation, supplemented with separate collection of national statistics, interviews with key stakeholders and findings in the research literature. The analyses are carried out in accordance with the steps in the guide for socioeconomic analyses from the Directorate for Financial Management (Direktoratet for økonomistyring, 2018) and the specific guidelines for analyses from the Norwegian Directorate of Health (Helsedirektoratet, 2012). In accordance with the framework, the analysis includes all types of effects, both monetized and non-monetized effects, as well as intended and unintended effects.

According to the current guidelines for conducting cost-benefit analyses in Norway (Direktoratet for økonomistyring, 2018), the consequences of telehealth will be measured against the zero alternative, which in this case involved standard clinical care.

Other pilot projects that may be partly overlapping with this study (for example, multidisciplinary care teams within primary care (Helsedirektoratet, 2018) and structured interdisciplinary follow-up teams (Helsedirektoratet, 2018)) have also been implemented in this same period. We will assess whether the various interventions "cannibalize" or "accelerate" the beneficial effects when interacting (decreasing vs. increasing marginal benefit).

We will assess the societal value based on the monetized effects, and then consider to what extent non-monetized effects contribute to the societal value. After an assessment of key uncertainties and distributional effects, the value of introducing telehealth can be compared with standard clinical care. The analysis of distributional effects will shed light on how benefits and costs are distributed between primary and specialist health services, as well as in the general population and for general practitioners, municipalities and health enterprises.

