**Thank you for your participation!**

## Appendix C: GP questionnaire

### Telehealth trial: Questionnaire for GPs with patients who are participating in the trial

#### Definition of telehealth monitoring

Telehealth monitoring is a broad concept that lacks a clear definition. When we refer to "telehealth monitoring" in this survey, we refer to telehealth monitoring provided within the framework of the test conducted by the Directorate of Health and your municipality. Below is a brief description:

Telehealth monitoring means that the patient can be followed up remotely by the health and care service using technological solutions. Users of remote monitoring can answer simple questions about their health status via a tablet, and take measurements related to their health status (eg blood pressure, weight, O2 saturation). The results are transferred from the measuring devices to the tablet so that the patient can easily see them and monitor their own results over time. The results are also transmitted digitally to a follow-up service. The response service / follow-up service contacts the patient in case of signs of deterioration and measurements beyond what are normal values for the individual. They provide medical professional support and guidance based on the patient's needs and plan for follow-up, and will, in consultation with the patient, consider whether they should contact their GP / emergency room.

Telehealth monitoring can provide better health and better patient experience through targeted use of health care resources. The distance follow-up initiative can come from a general practitioner, a hospital, the patient himself or another health professional. It is the GP who, in consultation with the patient, assesses whether distance follow-up may be appropriate and professionally justified for the individual. The GP will, together with the patient, nurse and any other relevant health personnel, prepare a plan for follow-up based on the patient's goals, symptom picture and risk of deterioration. This plan forms the basis for the follow-up content, frequency and contact point for the individual.

By "follow-up service", we mean the unit that monitors the registrations the users send via their tablets. The follow-up service has different names in different municipalities, including the follow-up service, the telemedicine center and the health guard

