### **Claims related to telehealth monitoring**

32. Consider the following claims regarding telehealth monitoring.

- Telehealth monitoring can contribute to unnecessary disease focus among some users
  - Strongly disagree
  - Disagree
  - Neither agree nor disagree
  - Agree
  - Strongly agree
- Telehealth monitoring can contribute to increased security for relatives
  - Strongly disagree
  - Disagree
  - Neither agree nor disagree
  - Agree
  - Strongly agree
- Telehealth monitoring can help to more accurately assess users' needs for health care
  - Strongly disagree
  - Disagree
  - Neither agree nor disagree
  - Agree
  - Strongly agree
- Telehealth monitoring can help to identify the need for health care that the user would otherwise not require
  - Strongly disagree
  - Disagree
  - Neither agree nor disagree
  - Agree
  - Strongly agree
- Telehealth monitoring can help save resources for the GP services
  - Strongly disagree
  - Disagree
  - Neither agree nor disagree
  - Agree
  - Strongly agree

33. What do you think are the biggest challenges for implementing telehealth monitoring as a national measure in the future?

34. Do you have any other comments related to telehealth monitoring?

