#### **Collaboration and interaction**

The goals of telehealth monitoring are improved patient experience, improved (or more stable) physical and mental health, and lower costs for the health care services. One way to achieve these goals is by improved collaboration and collaboration between different parts of the health care services.

In this section, we ask how you feel that the collaboration with other health care services related to telehealth monitoring works.

8. How does interaction with the following actors work related to the organization of telehealth monitoring in your municipality:

	Very poorly	Poorly	Neither poorly nor well	Well	Very well
Home care services (home nursing, BPA, everyday rehabilitation etc.)					
The GP service					
Specialist health service					

9. You have answered that the interaction with one or more actors works poorly or very poorly. Can you elaborate?

10. How does interaction with the following actors work related telehealth monitoring of each individual patient:

	Very poorly	Poorly	Neither poorly nor well	Well	Very well
Home care services (home nursing, BPA, everyday rehabilitation etc.)					
The GP service					
Specialist health service					

11. You have answered that the interaction with one or more actors works poorly or very poorly. Can you elaborate?

12. How do you feel that telehealth monitoring affects the coordination and consistency of the service provision of each individual patient?

- I find that the degree of coordination and coherence is reduced
- I find that there is no change in the degree of coordination and context
- I find that the degree of coordination and coherence is increasing

13. Do you have any further comments related to the interaction with other actors in the health service?

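### GP question 29 and follow-up staff question 16 have no answer for perceived worsening of users' physical health, mental health, security or coping, so worsening cannot be told apart from no effect

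*Combined protocol and SAP*

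**What the plan says.** Both staff questionnaires have a section on satisfaction and benefits for users, introduced with "In this section, we ask about how you perceive that telehealth monitoring affects the users". Within it, GP question 29 and follow-up staff question 16 use the same stem, "To what extent do you feel that telehealth monitoring contributes positively to users", for physical health, mental health, security and coping. Each line offers *Not at all*, three rising degrees of extent, and *Do not know*. GP question 30 and staff question 17 ask in the same format how far telehealth helps users become more involved in following up their illness.

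The definition at the start of the GP form contains the sentence "Telehealth monitoring can provide better health and better patient experience through targeted use of health care resources". The staff form has no such sentence. Each form has a goals statement before its collaboration section: "The goals of telehealth monitoring are better patient experience, better (or more stable) physical and mental health" for GPs and "The goals of telehealth monitoring are improved patient experience, improved (or more stable) physical and mental health" for staff.

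Section 6.4 describes an exploratory process evaluation that rests mainly on interviews, with survey data as a supplement. Section 6.5 builds the cost-benefit analysis partly on that evaluation and commits it to "both monetized and non-monetized effects, as well as intended and unintended effects". Table 4 schedules both staff surveys electronically for Fall 2019 and Spring 2021, with no control group for either.

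**The concern.** The section introduction promises to ask how telehealth affects users, but the main rating items can record only benefit or its absence. Some GPs or nurses may think monitoring makes patients more anxious, less secure or less able to cope. That view is what an analysis of unintended effects needs, and it has no answer option here. Neither survey has a comparison group that could reveal it indirectly, and some respondents are rating a service they run. Once collected in this form, the answers cannot be re-analysed to recover the missing direction.

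Security is the most exposed domain. Table 1 lists no security outcome compared between the arms. The patient questionnaire's item on feeling safer concerns tablet use, and disagreeing with it does not separate feeling the same from feeling less safe.

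**Working it through.** The plan states no figure on this point, so the check is mainly a reading of the forms.

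**Scale direction, item by item**
- GP 29 and staff 16 (four health-related domains): positive contribution only; the lowest substantive answer is *Not at all*.
- GP 30 and staff 17 (involvement): one-sided in the same way.
- GP 21 (time spent): significantly reduced to significantly increased, two-sided.
- GP 25 (interaction with other services): five points starting at "Much worse interaction" and ending at the opposite pole, two-sided.
- GP 26 and staff 12 (coordination): reduced, no change or increasing, two-sided.
- GP 31 (immediate-help appointments): reduction, no change or increase, two-sided.
- GP 32 and staff 18 (claims): both include "Telehealth monitoring can contribute to unnecessary disease focus among some users" with five agree/disagree options. This is an explicit harm item, but not a rating of any of the four domains.

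A two-sided format was therefore available and in use in the same instruments. It was not used for the four domains where perceived harm matters most.

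**What the answers can and cannot identify (assumed numbers)**

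Code the answers 0 (*Not at all*), 1, 2, 3. Suppose a perceived effect e on a scale from -3 to +3 is recorded as max(e, 0), meaning that those who see harm tick *Not at all*. Take recorded answers of 60% at 0, 25% at 1 and 15% at 2. The recorded mean is 0.25 × 1 + 0.15 × 2 = 0.55. Two different realities produce these same answers:
- All of the 60% see no effect. The true mean is 0.55.
- Of the 60%, 20% see no effect, 25% see -1 and 15% see -2. The true mean is 0.55 - 0.25 × 1 - 0.15 × 2 = 0.

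In a net-harm example with 25% at -2, 35% at -1, 20% at 0, 15% at +1 and 5% at +2:
- true mean = -0.50 - 0.35 + 0.15 + 0.10 = -0.60
- recorded mean = 0.15 + 0.10 = 0.25
- recorded *Not at all* = 25% + 35% + 20% = 80%

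These distributions are invented to show the mechanism. The documents give none, so they say nothing about how large the effect would be in this trial.

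**The case against.** The case against giving this much weight is substantial, and most of it stands.

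- A reader might infer that the two forms leave no room for negative views. They do leave room: both have the disease-focus item, a two-sided coordination item and open questions on challenges and other comments, and the GP form also has two-sided items on time and immediate-help appointments. Table 5 adds interviews on safety and coping with users, on security with relatives, and on costs and benefits with GPs and follow-up staff.
- A reader might infer that both groups answer after promotional text. The benefit sentence is in the GP form only. The staff form states goals, which is not a claim of benefit, and the introduction to the rating section is neutral. The direction and size of any effect of the GP sentence are not shown.
- A reader might infer that every perceived harm becomes *Not at all* and that a net result is inflated. *Do not know* is offered and an item can be left blank. The plan defines no score or net share for these items.
- The main effects do not depend on them. EQ-5D can worsen and is compared between arms, as are satisfaction, coping and cost. The patient form also has feelings items such as worry and calm, sent to both groups, and tablet items that ask about drawbacks.

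What remains is narrower: none of these other sources gives a structured staff rating of worsening in the four domains, and the surveys are meant to add breadth beyond a limited number of interviews (section 8.2.2).

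**Conclusion.** The point holds as a limited weakness in two supplementary questionnaires. Perceived worsening of physical health, mental health, security or coping has no answer option in GP question 29 or staff question 16, and cannot be separated from no effect. The same gap affects the involvement items. It touches the exploratory process evaluation and the non-monetized and unintended-effects inputs to section 6.5. It does not bias the randomized comparisons. Its size cannot be estimated from the documents, because the share of respondents who perceive harm, and how they would answer, is unknown. Low severity; worth correcting because the correction is easy and the information cannot be recovered from these answers later.

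**What to change.** 1. Reword GP question 29 and staff question 16 as *How does telehealth monitoring affect users' physical health / mental health / security / coping?*, with the five-point worse-to-better scale of GP question 25 plus *Do not know*.
2. Make GP question 30 and staff question 17 two-sided in the same way.
3. Report the worse and better shares separately for each domain.
4. In the GP form only, remove the benefit sentence from the definition or balance it.

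This adds no length and needs no extra staff. Section 12.6 describes registration in summer 2019 as still to come, which suggests that the Fall 2019 survey could be corrected before dispatch. If it has already been sent, the reworded items lose direct comparability between Fall 2019 and Spring 2021, and the report should say so.

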### **Claims related to telehealth monitoring**

32. Consider the following claims regarding telehealth monitoring.

- Telehealth monitoring can contribute to unnecessary disease focus among some users
  - Strongly disagree
  - Disagree
  - Neither agree nor disagree
  - Agree
  - Strongly agree
- Telehealth monitoring can contribute to increased security for relatives
  - Strongly disagree
  - Disagree
  - Neither agree nor disagree
  - Agree
  - Strongly agree
- Telehealth monitoring can help to more accurately assess users' needs for health care
  - Strongly disagree
  - Disagree
  - Neither agree nor disagree
  - Agree
  - Strongly agree
- Telehealth monitoring can help to identify the need for health care that the user would otherwise not require
  - Strongly disagree
  - Disagree
  - Neither agree nor disagree
  - Agree
  - Strongly agree
- Telehealth monitoring can help save resources for the GP services
  - Strongly disagree
  - Disagree
  - Neither agree nor disagree
  - Agree
  - Strongly agree

33. What do you think are the biggest challenges for implementing telehealth monitoring as a national measure in the future?

34. Do you have any other comments related to telehealth monitoring?

### **Background information**

35. In which municipality do you work?

- Bodø
- Eid
- Kristiansand
- Larvik
- Oslo
- Ullensaker
- Gjerdrum
- Other municipality in Agder
- Other municipality

36. In which urban district do you work?

- Alna
- Bjerke
- Frogner
- Gamle Oslo
- Grorud
- Grünerløkka
- Nordre Aker
- Nordstrand
- Sagene
- St. Hanshaugen
- Søndre Nordstrand
- Ullern
- Vestre Aker
- Østensjø

37. Do you participate as a GP in the trial of primary health care teams?

- Yes
- No

38. What is your gender?

- Male
- Female

39. How old are you?

- Younger than 30 years
- 30-39 years
- 40-49 years
- 50-59 years
- 60 years or older

40. How many years have you worked as a GP?

- Less than 1 year
- 1-2 years

- 3-4 years
- 5-9 years
- 10 years or more

41. What is your highest level of completed education?

- Cand. Med.
- Authorized physician LIS1
- Specialist in general medicine
- Specialist in other domain

42. Do you have any comments related to this survey?

## Appendix D: Follow-up service questionnaire

### Telehealth trial: Questionnaire for employees in the follow-up service

#### Inclusion and exclusion criteria:

The target group of the telehealth trial is patients with chronic diseases, with medium or high risk of worsening of one's condition, risk of re-hospitalization or increased need for health and care service. These patients have a high consumption of health care services and the target group consist largely of patients with non-communicable chronic diseases such as diabetes, colic, cardiovascular disease, mental disorders and cancer. This group often has several diagnoses, complex and large needs, and in need of follow-up of their diseases.

Patients who are not competent to consent, patients who cannot use the tablet or the measuring devices, together with patients with substance use disorders, shall not be included in the trial.

#### In this part of the questionnaire we ask how you experience these inclusion and exclusion criteria.

1. To what extent do you experience that the inclusion and exclusion criteria are well suited for telehealth monitoring?
  - Not at all
  - To a small extent
  - To some extent
  - To a large extent
  - To a very large extent
2. You have stated that you do not at all, or to a small extent, feel that the inclusion criteria for participation in the telehealth trial are suitable. Can you elaborate?
3. Do you have any comments related to the inclusion and exclusion criteria for the telehealth trial?

#### The general practitioner's assessment of the patient's suitability for participation in the trial of medical distance follow-up:

In the telehealth trial the Directorate of Health has decided that the general practitioner, as a medical professional responsible for the patients on his/her list, must assess whether each proposed patient is suited to participate in the trial. In this section we ask about your opinions on this.

4. Do you think it is right that it is mandatory that the GP participates in the assessment of the patient's suitability for telehealth monitoring?
  - Yes
  - No
5. You answered that you do not think it is right that it is mandatory that the GP participates in the assessment of the patient's suitability for telehealth monitoring. Can you elaborate?

#### Your time spent:

In this part we ask about we ask you how you allocate your working time to different tasks. Think of an average work week.

6. How large is your overall job percentage related to telehealth follow-up?

- 0-20
- 21-40
- 41-60
- 61-80
- 81-100

7. Indicate (approximately) the percentage of your total working time spent on the following tasks related to telehealth monitoring? [indicate one number per line]

- Recruiting new patients (including information meetings, training/instruction, ancillary working and interdisciplinary work with the patients plan for follow-up)
- Phone calls with patients
- Assessment of measurements / results
- Communication with the GP (not interdisciplinary meetings in connection to starting the patient up with telehealth monitoring), other primary health care or specialist health care
- Other

